### 16. DATA HANDLING AND DATA MANAGEMENT

#### 16.1 Data confidentiality

Information about study patients will be kept confidential and managed under the applicable laws and regulations. Those regulations require a signed patient informed consent form informing the patient of the following:

- what protected health information (PHI) will be collected from patients in this study;
- who will have access to that information and why;
- who will use or disclose that information;
- the rights of a research patient to revoke their authorization for use of their PHI.

In the event that a patient revokes his / her consent to collect or use PHI, the investigator, by regulation, retains the ability to use all information collected prior to the revocation of patient authorization. For patients that have revoked authorization to collect or use PHI, attempts should be made to obtain permission to collect at least survival status (i.e. that the patient is alive) at the end of their scheduled study phase.

The data collection system for this study uses built-in security features to encrypt all data for transmission in both directions, preventing unauthorized access to confidential participant information. Access to the system will be controlled by individually assigned user identification codes and passwords, made available only to authorized personnel who have completed prerequisite training.

#### 16.2 Use and completion of the electronic case report forms (eCRF)

An electronic case report form will be completed for each study patient. It is the responsibility of the investigator to ensure the accuracy, completeness, legibility and timeliness of the data reported in the patient's eCRF which have been designed by the sponsor to record all observations and other pertinent data to the clinical investigation.

Source documentation supporting the eCRF data should indicate the patient's participation in the study and should document the dates and details of study procedures, adverse events and patient status.

The investigator, or designated representative, should complete the eCRF pages as soon as possible after information is collected, preferably within 5 to 7 business days after an

examination, treatment, or any other study procedure but not later than prior to the next visit. Any outstanding entries must be completed immediately after the final examination.

### 16.3 Data management

The data management will be performed with SecuTrial®, a proprietary remote data entry system, which is maintained by the Clinical Trials Unit at the University Medical Center Göttingen. Details on data management (procedures, responsibilities, etc.) will be described in a data management plan prior to the study start. During the study, the performance of data management and any deviations from the data management plan will be documented in a data management report. The technical specifications of the database and the e-forms (variable names, attributes and data entry checks) will be described in a corresponding data base plan. Before any data entry performed, the study database and edit checks of the e-forms will be validated. Data entry personnel will not be given access to the study data base until they have been trained and signed an access form. An audit trail provides a data history which data were entered, changed or deleted, by whom and when.

SAS software will be used to review the data for completeness, consistency and plausibility. The checks to be programmed will be specified beforehand in a data validation plan. After running the check programs, the resulting queries will be sent via the system to the investigator / site personnel for correction or verification of the documented data. Data corrections will be entered directly into SecuTrial® by the responsible investigator or designated person.

## **17. STUDY MONITORING**

## 17.1 Investigators responsibilities

Investigator responsibilities are set out in the ICH-GCP and in the local regulations. The sponsor staff or an authorized representative will evaluate and approve all investigators who in turn will select their staff.

The investigator should ensure that all persons assisting with the study are adequately GCP trained and informed about the protocol, amendments, study treatments, as well as study-related duties and functions. The investigator should maintain a list of sub-investigators and other appropriately qualified persons to whom he or she has delegated significant study-related duties.

The investigator is responsible for keeping a record of all patients who sign an informed consent document and are screened for entry into the study. Patients who fail screening must have the reason(s) recorded in the patient's source documents.

The investigator, or a designated member of the investigator's staff, must be available during monitoring visits to review data, resolve queries and allow direct access to patient records (e.g.

medical records, office charts, hospital charts, and study-related charts) for source data verification. The investigator must ensure timely and accurate completion of eCRFs, queries and SAE-reports.

## 17.2 Sponsor responsibilities

The sponsor (University Hospital Ulm) or an authorized representative of this study has responsibilities towards the national legislature to take all reasonable steps to ensure the proper conduct of the study as regards patient safety, ethics, study adherence, integrity and validity of the data recorded in the eCRF. Thus, the main duty of the coordinating investigator and of his clinical research support team is to help the investigators maintain a high level of ethical, scientific, technical and regulatory quality in all aspects of the study.

## 17.3 Source document requirements

According to the ICH-GCP, the study monitor has to check the CRF entries against the source documents. The consent form will include a statement by which the patients allow the sponsor's duly authorized personnel (study monitoring team) to have direct access to source data which supports data on the case report forms (e.g. patient's medical file, appointment books, original laboratory records, etc.). These personnel, bound by professional secrecy, will not disclose any personal identity or personal medical information.

## 17.4 Monitoring visits

Risk-based monitoring will be done according to ICH-GCP E6 and standard operating procedures to verify that patients' rights and wellbeing are protected, reported study data are accurate, complete and verifiable from source documents and that the study is conducted in compliance with the currently approved protocol / amendment, with ICH-GCP and with the applicable regulatory requirements to ensure patient safety and integrity of clinical study data.

At regular intervals during the study, the study sites will be contacted, through site visits (on-site visits) or telephone calls (remote visits), by a representative of the monitoring team or sponsor to review study progress, investigator and patient adherence to study requirements and any emergent problems. The investigator must give the monitor access to all relevant source documents to confirm their consistency with the eCRF entries (source data verification, SDV). During monitoring visits, the following points will be scrutinized with the investigator: patient informed consent, inclusion and exclusion criteria, patient recruitment and follow-up, patient compliance to the study treatment, study drug accountability, concomitant therapy use, evaluations of response, serious / non-serious adverse event documentation and reporting, and quality of data. The number of contacts will depend on the characteristics of the respective study site, e.g. the number of recruited patients. All study specific monitoring procedures (on-site /

remote), monitoring visit frequency and extent of SDV will be predefined in a study specific monitoring manual.

## 18. ETHICAL AND REGULATORY STANDARDS

This clinical study was designed, shall be implemented and reported in accordance with the ICH-GCP, with applicable national and international regulations and with the ethical principles laid down in the Declaration of Helsinki.

Before initiating the clinical study, the sponsor should submit the protocol and any required application(s) to the appropriate CA for review, acceptance, and / or permission, as required by the applicable regulatory requirements.

The protocol and the proposed informed consent form must be reviewed and approved by a properly constituted EC before study start. A signed and dated statement that the protocol and informed consent have been approved by the EC must be available prior to initiation of the study.

The sponsor must submit this study to country EC and to CA and forward a copy of written approvals / advices signed to the investigators (in the ISF).

### 18.1 Informed consent

It is the responsibility of the investigator to obtain informed consent in compliance with national requirements from each patient prior to any study related procedures or, where relevant, prior to evaluating the patient's suitability for the study.

The informed consent document used by the investigator for obtaining patient's informed consent must be reviewed and approved by the EC. The documents must be available in a fluent language of the patient to include the patient into the study.

The investigator must explain in a fluent language of the patient (e.g. using official translators and informed consent forms in a fluent language of the patient) the aims, methods, reasonable anticipated benefits and potential hazards of the study and any discomfort it may entail. Patients will be informed that they are free not to participate in the study and that they may withdraw consent to participate at any time. They will be told which alternative treatments are available if they refuse to take part and that such refusal or withdrawal will not prejudice future treatment.

If the withdrawal is caused by any adverse drug event, the patient should inform the investigator about this fact. All data collected before the time point of withdrawal remain within the study database. Consent will be sought from the patient, in order to be allowed to:

- report further major outcome information (e.g. efficacy data)
- guarantee the safety of a patient
- comply with requirements to submit complete documents for authorization

Documentation that informed consent occurred prior to the study patient's entry into the study and of the informed consent process should be recorded in the study patient's source documents including the date.

The original informed consent document signed and dated by the study patient and by the person having informed and obtained consent from the study patient prior to the study patient's entry into the study, must be maintained in the ISF and a copy given to the study patient. In addition, if a protocol is amended and it impacts on the content of the informed consent, the informed consent document must be revised. Study patients undergoing treatment when the revised patient information is implemented must be re-informed and should re-consent with the revised version of the informed consent document. Patients within follow up must only reconsent if essential or safety relevant information were changed in the patient information form (in consultation with the responsible EC and sponsor). The revised informed consent document signed and dated by the study patient and by the person having informed and obtained consent form the study patient must be maintained in the ISF and a copy given to the study patient. No compensation will be paid to the patients by the sponsor.

## **19. ADMINISTRATIVE PROCEDURES**

### 19.1 Secrecy agreement

All goods, materials, information (oral or written) and unpublished documentation provided to the investigators (or any company acting on their behalf) and the patient case report forms are the exclusive property of the sponsor.

They may not be given or disclosed by the investigator or by any person within his team either in part or in totality to any unauthorized person without the prior written formal consent of the sponsor.

It is specified that the submission of this study and other necessary documentation to the EC or a like body is expressly permitted, the EC members having the same obligation of confidentiality.

The investigator shall consider all information as confidential and shall take all necessary measures to ensure that there is no breach of confidentiality in respect of all information accumulated, acquired or deduced in the course of the study, other than that information to be disclosed by law.

## 19.2 Record retention in study sites

The investigator must maintain all study records including the investigator site file, patient files and other source data for the maximum period of time permitted by the hospital, institution or private practice. However national regulations should be considered, the longest time having to be considered.

The investigator is required to arrange for the retention of the patient identification codes in accordance with applicable law. If longer storage periods are needed, the sponsor will inform the site prior to the end of the archival time. The sponsor is responsible for archiving the trial master file in accordance with applicable law.

### 19.3 Ownership of data and use of the study results

The sponsor has the ownership of all data and results collected during this study. In consequence the sponsor reserves the right to use the data of the present study, either in the form of case report forms (or copies of these), or in the form of a report, with or without comments and with or without analysis, in order to submit them to the CA and EC of any country (final clinical study report).

## 19.4 Publication

The final publication of the study results will be written by the coordinating investigator and the national co-coordinating investigators on the basis of the statistical analysis. A draft manuscript will be submitted to all co-authors for review. After revision by the co-authors, the manuscript will be sent to a peer reviewed scientific journal. Authors of the manuscript will include the coordinating investigator and the national co-coordinating investigators, investigators who have included more than 3% of the evaluable patients in the study (by order of inclusion), the statisticians, and others who have made significant scientific contributions.

Interim publications or presentations of the study may include demographic data, overall results and prognostic factor analyses. Any publication, abstract or presentation based on patients included in this study must be approved by the coordinating investigator. This is applicable to any individual patient registered in the study, or any subgroup of the study patients. Such a publication cannot include an analysis of any of the study end-points unless the final results of the study have already been published.

Prior to submission for publication of any manuscript, poster, presentation, abstract, or other written or oral material describing the results of this study, the sponsor shall provide supporting companies 30 calendar days to review the manuscript and 15 calendar days to review any poster, presentation, abstract, or other written or oral material derived from the study.

#### 19.5 Insurance compensation

If required according to the national regulations for each participating country, the sponsor of the study will obtain insurance coverage for eventually occurring damage caused by the treatment or any actions taken according to the treatment plan. A certificate of insurance will be provided to the investigator in countries in which this document is required. The investigator, or an individual who is designated by the investigator, will inform the patient of the existence of the insurance, including the obligations arising from it. The study patients must be given access to the insurance documents and, on request, a copy of the general conditions of insurance.

### 19.6 Audits and inspections by regulatory agencies

For the purpose of ensuring compliance with good clinical practice and regulatory guidelines it may be necessary to conduct a site audit or an inspection.

By participating in this study and signing the study contract, the investigator agrees to allow the sponsor and its representative, and competent authorities to have direct access to his study records for review. These personnel, bound by professional secrecy, will not disclose any personal identity or personal medical information.

These audits or inspections involve review of source documents supporting the adequacy and accuracy of data gathered in eCRF, review of documentation required to be maintained, and checks on drug accountability.

The investigator needs to inform the sponsor immediately of an inspection requested by a CA. The investigator is responsible for providing / giving access to source data / documents to auditors / inspectors. The sponsor will in all cases help the investigator prepare for an inspection.

#### 19.7 Clinical study report

The sponsor will inform the CA and EC about the end of the study within 90 days following the end of study. A study report will be prepared under the responsibility of the sponsor less than one year after the end of the study and forwarded to the EudraCT database, CA, EC and the supporting companies.

#### 19.8 Study Amendments

No changes or amendments to this study may be made by the investigator or by the sponsor after the study has been agreed to and signed by both parties unless such change(s) or amendment(s) have been fully discussed and agreed upon by the coordinating investigator, Amgen, Janssen and the sponsor.

Any change agreed upon will be recorded in writing, the written amendment will be signed by the coordinating investigators, by the sponsor and study statistician, who is responsible for study planning.

Approval / advice of amendments by EC and CA are required prior to their implementation, unless there are overriding safety reasons.

## 19.9 Contract of Investigation

The participating institutions are selected by the coordinating investigator, based on the proven qualification in the framework of previous studies in the cooperative groups. The clinical study sites will document their appropriate qualification and capacities for taking part in the study, in order to allow for a qualified decision of the EC on their participation.

The investigator of every participating study site has to sign the contract before start of the study. With this contract the investigator agrees to treat all patients who have been admitted to the participating study site during active study-recruitment fulfilling the inclusion criteria and not the exclusion criteria after giving an informed consent and registration at the study office within the present study. Additionally, he agrees to document all required study relevant data into the specific eCRFs.

# 19.10 Financing

The coordinating investigator and the sponsor will take care of the financing / funding of the study. The study will be funded in part by Amgen and by Janssen. The study drug, "Ibrutinib" will be provided by Janssen free of charge, the study drug "Carfilzomib" by Amgen free of charge.

## 21. APPENDICES

## 21.1 Appendix A: Modified Response Criteria according to Owen et al

Response category	Definition
Complete response (CR)	
 
Absence of serum monoclonal IgM protein by immunofixation
 
Normal serum IgM level
 
Complete resolution of lymphadenopathy and splenomegaly if present at baseline
 
Morphologically normal bone marrow aspirate and trephine biopsy
 

Very Good Partial Response (VGPR)	
 
Monoclonal IgM protein is detectable
 
≥90% reduction in serum IgM level from baseline
 
Decreased lymphadenopathy / splenomegaly if present at baseline
 
No new signs or symptoms of active disease
 

Partial response (PR)	
 
Monoclonal IgM protein is detectable
 
> 50% but < 90% reduction in serum IgM level from baseline
 
Decreased lymphadenopathy / splenomegaly if present at baseline
 
No new signs or symptoms of active disease
 

Minor response (MR)	
 
Monoclonal IgM protein is detectable
 
> 25% but < 50% reduction in serum IgM level from baseline
 
No new signs or symptoms of active disease
 

Stable disease (SD)	
 
Monoclonal IgM protein is detectable
 
< 25% reduction and < 25% increase in serum IgM level from baseline
 
No progression in lymphadenopathy / splenomegaly
 
No new signs or symptoms of active disease
 

Progressive disease (PD) 	
 
≥ 25% increase in serum IgM level from lowest nadir (with confirmation) and / or
 
progression in clinical features attributable the disease. An absolute increase of at least 5 g/l is required to define progression when the IgM level is the only applicable criterion.
 

1. Nadir for serum IgM is defined as the lowest serum IgM value obtained at any time from baseline onwards with the exception that serum IgM levels post-plasmapheresis will not be considered for up to 35 days.

2. Sum of the products of multiple lymph nodes (as evaluated by CT scans) or the longest diameter of one target lymph node

3. Serum protein electrophoresis, nephelometry or densitometry (whichever is used for an individual patient) and immunofixation have to be repeated at least 6 weeks later in case of complete response to confirm CR.

4. Progression should be confirmed by a second measurement after 7 to 14 days.

5. Baseline is the IgM value at C1D1.

6. When interrupting ibrutinib, some patients may experience an IgM rebound, which must be carefully differentiated from progression.

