### 10.2 Inclusion criteria

Each patient must meet the following inclusion criteria to be enrolled in this study:

- Proven clinicopathological diagnosis of WM as defined by consensus panel one of the Second IWWM. Histopathology has to occur before randomization within the last 4 months. In addition, pathological specimens have to be sent to the pathological reference center prior to randomization for the determination of the mutational status of MYD88 and CXCR4 (if not already known). Immunophenotyping will be performed in each center and archived locally. The positivity for CD20 can be assumed from any previous bone marrow immunohistochemistry or flow cytometry analysis performed up to 4 months prior to enrollment. Flow cytometry of bone marrow and blood cells will include at least one double staining and assess the disease specific expressions.
- De novo or relapsed / refractory WM independent of the genotype.
- Patients must have at least one of the following criteria to start study treatment as partly defined by consensus panel criteria from the Seventh IWWM:
  - Recurrent fever, night sweats, weight loss, fatigue.
  - Hyperviscosity.
  - Lymphadenopathy which is either symptomatic or bulky (≥ 5 cm in maximum diameter).
  - Symptomatic hepatomegaly and / or splenomegaly.
  - Symptomatic organomegaly and / or organ or tissue infiltration.
  - Peripheral neuropathy due to WM.
  - Symptomatic cryoglobulinemia.
  - Cold agglutinin anemia.
  - o IgM related immune hemolytic anemia and / or thrombocytopenia.
  - Nephropathy related to WM.

- o Amyloidosis related to WM.
- Hemoglobin ≤ 10 g/dL (patients should not have received red blood cells transfusions for at least 7 days prior to obtaining the screening hemoglobin).
- Platelet count < 100 x  $10^{9}$ /L (caused by BM infiltration of the lymphoma).
- $\circ$  Serum monoclonal protein > 5 g/dL, even with no overt clinical symptoms.
- IgM serum concentration  $\geq$  5 g/dl.
- $\circ~$  and other WM associated relevant symptoms.
- World Health Organization (WHO) / ECOG performance status ≤ 2.
- Left ventricular ejection fraction ≥ 40% as assessed by transthoracic echocardiogram (TTE).
- Other criteria
  - Age  $\geq$  18 years (male and female).
  - Life expectancy > 3 months in the opinion of the investigator.
  - Baseline platelet count ≥ 50 x10^9/L, absolute neutrophil count ≥ 0.75 x 10^9/L (if not due to BM infiltration by the lymphoma).

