## 10.3 Exclusion criteria

The presence of the following criteria will exclude a patient from enrolment:

- Previous treatments with following substances:
  - Prior exposure to Ibrutinib or other BTK inhibitors.
  - Prior exposure to Carfilzomib. Prior exposure to other proteasome inhibitors is allowed if the patients were not refractory, that is, had a remission (at least minor response) duration of ≥ 6 months. Prior plasmapheresis and short-term administration of corticosteroids ≤ 6 weeks administered at a dose equivalent to ≤ 20 mg/day of prednisone is also allowed.
- Serious medical or psychiatric illness (especially undergoing treatment) likely to interfere with participation in this clinical study.
- Active HIV, HBV or HCV infection (see protocol section 12.4.12.9).
- Central Nervous System involvement by lymphoma.
- History of a non-lymphoid malignancy except for the following: adequately treated local basal cell or squamous cell carcinoma of the skin, cervical carcinoma in situ, superficial bladder cancer, asymptomatic prostate cancer without known metastatic disease and with no requirement for therapy or requiring only hormonal therapy and with normal prostate specific antigen for ≥ 1 year prior to randomization, other Stage 1 or 2 cancer treated with a curative intent and currently in complete remission, for ≥ 3 years.
- Uncontrolled illness including, but not limited to:
  - Uncontrolled diabetes mellitus (as indicated by metabolic derangements and / or severe diabetes mellitus related uncontrolled organ complications).
  - Chronic symptomatic congestive heart failure (Class NYHA III or IV) or LVEF < 40%.
  - Unstable angina pectoris, angioplasty, stenting, or myocardial infarction within 6 months prior to randomization.
  - Clinically significant cardiac arrhythmia that is symptomatic or requires treatment, or asymptomatic sustained ventricular tachycardia.
  - Known pericardial disease.

- Malabsorption syndrome, disease significantly affecting gastrointestinal function, or resection of the stomach or small bowel, ulcerative colitis, symptomatic inflammatory bowel disease, or partial or complete bowel obstruction.
- Cardiac amyloidosis.
- Recent major surgery within 30 days prior to randomization.
- Known cirrhosis (meeting child-pugh stage C).
- Approved or investigational anticancer treatment within 21 days prior to randomization.

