## 12.2 Active treatment phase

Details of the procedures performed during the treatment phase are described in the flowcharts and in the sections below. All patients will be closely monitored for adverse events, laboratory abnormalities, ECG abnormalities and response. Clinical evaluations and laboratory assessments may be repeated more frequently, if clinically indicated.

Additionally, for the first 10 patients in treatment arm A (Carfilzomib and Ibrutinib) laboratory assessments will be performed on day 8 and 15 of the first 6 cycles. Also, an ECG will be performed on day 15 during the first 6 cycles.

If a patient completes the active treatment phase, an end of treatment visit 30 calendar days after last dose of study treatment has to be performed.

If progression occurs at any time point of the study (i.e. during therapy or during follow up) the assessments described in the flowchart have to be performed (could be combined with another visit of the flow chart, e.g. end of treatment or follow up, depending on what applies). Relapse / progression will be determined by the modified response criteria as published (appendix 21.1). A pathological confirmation by biopsy of the bone marrow or lesion if present should be done if possible.

IgM levels obtained more than 35 days after plasmapheresis can be used in response determination. If disease progression is suspected solely based on the results of a single examination or a single laboratory parameter, this finding should be confirmed by a subsequent evaluation at least within 4 weeks from the first finding. Additional hematologic parameters, radiographic evaluation and bone marrow biopsy should be performed at the discretion of the investigator to confirm progressive disease if indicated.

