## 12.4.12 Laboratory tests (local laboratory at the site)

Blood tests and urinalysis include the routine parameter listed below and will be scheduled according to the laboratory flowcharts (see appendix 21.4 and 21.5) and in addition as clinically indicated. In case of cytopenia the frequency of blood samples would be increased from the 25th cycle (Arm A) and 14th cycle (Arm B) to once a month. Test results from the screening visit can be used for Cycle 1, day 1 in the discretion of the investigator (depending on local standards and e.g. the timeframe between screening laboratory and day 1).

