## 14.5 Analysis populations

## 14.5.1 Core Analysis Population

The core analysis population consists of all patients randomized in the study evaluated in the group they were randomized to. Patients with missing or unevaluable response assessment12 months after randomization (primary endpoint) will be excluded from analysis of the primary outcome. Patients who progressed or died within 12 months from randomization are not in CR/VGPR at this time point and are thus classified as non-responders (i.e. CR/VGPR="no"). We do not impute missing or unevaluable response assessment because we expect those missing values as missing at random since regular follow-up for lymphoma progression is foreseen also in case of early treatment discontinuation. We will make sure by communication and monitoring that the follow-up schedule will be maintained in case of early treatment discontinuation irrespective of the treatment group. As a sensitivity analysis for the primary outcome, we will perform a conservative imputation of the CR/VGPR rate at 12 months from randomization by defining patients alive without progression and with missing or unevaluable response assessment at this time point as non-responders (i.e. CR/VGPR="no"). The group comparisons of secondary efficacy outcomes represent further sensitivity analyses with different approaches to missing or unevaluable response assessment at 12 months from randomization (e.g. last observation carried forward in best response, counting treatment discontinuation as event in TTF, and censoring at last staging in PFS).

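### Baseline IgM is fixed at cycle 1 day 1 with no plasmapheresis exception, so a true VGPR near the 90% limit can be scored as PR after a recent exchange

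*Protocol*

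**What the plan says.** The primary endpoint is CR or VGPR at 12 months from randomization. In Appendix 21.1, VGPR requires "≥90% reduction in serum IgM level from baseline", and footnote 5 defines that baseline: "Baseline is the IgM value at C1D1". No exception is attached.

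The protocol recognises elsewhere that plasma exchange distorts IgM:

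- Appendix 21.1, footnote 1, defines the nadir used for progression with the exception that "serum IgM levels post-plasmapheresis will not be considered for up to 35 days".
- Section 12.2 states: "IgM levels obtained more than 35 days after plasmapheresis can be used in response determination".

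Recent exchange before entry is foreseeable. "Hyperviscosity" is one of the criteria for starting treatment in section 10.2. Section 10.3 lists "Prior plasmapheresis and short-term administration of corticosteroids" as allowed; the limits given there concern the corticosteroids, and no interval since the last exchange is set.

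Section 12.4.12 adds: "Test results from the screening visit can be used for Cycle 1, day 1 in the discretion of the investigator". In Table 1 this permission is repeated in the footnotes for haematology, chemistry and coagulation, and in Table 2 for chemistry and coagulation. The quantitative immunoglobulin row carries no such footnote in either table.

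**The concern.** The 35-day principle is applied to one end of the IgM comparison but not to the other. Footnote 1 protects the nadir and section 12.2 addresses response determination, while the baseline is tied to a calendar visit whatever happened in the preceding weeks. If an exchange has lowered IgM by cycle 1 day 1, the denominator of the VGPR criterion is too small and the patient must reach a deeper true reduction to be counted. The error runs in one direction: VGPR is under-called. The same baseline serves PR, MR and stable disease, so the secondary response rates are exposed too.

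**Working it through.** **1. The plan's own figure.** Section 14.2 gives 16% against 35%, one-sided alpha 0.10, power 80%, chi-square test. With pooled variance and no continuity correction:

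- n per arm = [1.2816·√(2·0.255·0.745) + 0.8416·√(0.16·0.84 + 0.35·0.65)]² / 0.19² = 1.296² / 0.0361 ≈ 46.5, so 47 per arm and 94 in total, as stated.
- Power at 47 per arm is 80.3%.
- 94 / 0.95 = 98.9, so 99, as stated.

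**2. One patient.** The IgM values are assumed; 60 g/L is compatible with the entry criterion of at least 5 g/dL (50 g/L).

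- Before exchange 60 g/L, cycle 1 day 1 36 g/L (a 40% shortfall), month 12 5 g/L.
- From the pre-exchange value: 1 − 5/60 = 91.7%, in the VGPR range.
- From cycle 1 day 1: 1 − 5/36 = 86.1%, in the PR range.
- VGPR limits: 0.1 × 60 = 6.0 g/L against 0.1 × 36 = 3.6 g/L. Only month-12 values above 3.6 and up to 6.0 g/L change class.

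**3. General form.** Let r be the share by which IgM at cycle 1 day 1 lies below the pre-exchange level. A measured 90% fall then needs a true fall of 1 − 0.10·(1 − r). The value of r is assumed.

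| r | True fall needed for VGPR | A true 92% fall reads as |
|---|---|---|
| 20% | 92% | 90.0% |
| 30% | 93% | 88.6% |
| 40% | 94% | 86.7% |
| 50% | 95% | 84.0% |
| 60% | 96% | 80.0% |

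CR rests on normal IgM, negative immunofixation, resolved nodes and spleen, and normal marrow. It uses no percentage of baseline IgM, so it does not move.

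**4. Effect on the trial.** Let f be the share of patients whose cycle 1 day 1 falls within 35 days after exchange, and m the share of their VGPRs that are missed. Both are assumed. Both arms' rates are multiplied by (1 − f·m), and power is recomputed at 47 per arm.

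| f | m | Rates, A and B | Power |
|---|---|---|---|
| 0 | – | 35.0%, 16.0% | 80.3% |
| 5% | 0.5 | 34.1%, 15.6% | 79.3% |
| 10% | 0.5 | 33.3%, 15.2% | 78.2% |
| 10% | 1 | 31.5%, 14.4% | 75.9% |
| 20% | 1 | 28.0%, 12.8% | 71.1% |

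The last two rows are outer bounds. They require every VGPR in affected patients to be lost, whereas step 2 shows that only those near the limit change class.

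**The case against.** The strongest reply is that this is a wording gap with little consequence. The term response determination in section 12.2 could be read to include the baseline, which would leave only a fallback rule to be written, and such rules often sit in an SAP. The patient example is constructed to land in the narrow window that changes class. No frequency of recent exchange is given. Exchange before treatment is balanced by randomization, so the type I error is not inflated.

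Most of this stands, and it limits the size of the point. The SAP argument does not remove it: the protocol itself fixes the baseline in the response criteria, and a different SAP rule would contradict that footnote.

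A reader might infer three stronger claims, and the documents support none of them.

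- *That the protocol bars such IgM values as a baseline.* Section 12.2 grants a permission for later values; a ban is only its converse. The one explicit exclusion, in footnote 1, concerns the nadir.
- *That these patients drop out of the primary analysis.* Section 14.5.1 says that patients with a missing or unevaluable 12-month response "will be excluded from analysis of the primary outcome". It does not call a recently exchanged patient unevaluable, and footnote 5 always supplies a baseline if IgM is drawn at cycle 1 day 1.
- *That the baseline is chosen with knowledge of the arm and is therefore biased.* Allocation is indeed known by then. However, the flowcharts do not attach the screening substitution to immunoglobulins, screening IgM is taken on day −7 to 0, and any choice precedes all response data. What remains is an ambiguity about whether the general sentence in section 12.4.12 reaches IgM.

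**Conclusion.** The point holds as an inconsistency in the definition behind the primary endpoint. For a patient exchanged within 35 days before cycle 1 day 1, footnote 5 can use an artificially low denominator, and a true VGPR near 90% is then counted as PR. The error under-calls VGPR in both arms, is non-differential in expectation and leaves CR alone. Under the moderate assumptions (5–10% of patients affected, half of their VGPRs missed), power falls from 80.3% to 79.3–78.2%. The protocol gives neither the frequency of recent exchange nor the depth of the IgM shortfall, so these are scenarios and not estimates. The sample size is reproduced and need not change. The correction is worth making because it is cheap and concerns the primary endpoint.

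**What to change.** Amend footnote 5 of Appendix 21.1 along these lines: baseline is the IgM value at cycle 1 day 1 unless that day falls within 35 days after plasmapheresis. In that case, baseline is the last IgM before the exchange, from the same laboratory and by the same method (as section 12.4.13 asks for serial IgM), no older than a stated maximum age, and taken after the last prior anti-lymphoma therapy. Without the last two conditions, an old value could over-credit response. If no such value exists, use cycle 1 day 1, flag the patient, and examine the effect in a sensitivity analysis.

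In the same amendment, state whether the screening substitution in section 12.4.12 applies to IgM, and align footnotes 1 and 5 with section 12.2 so that one 35-day rule governs baseline, nadir and response values in both arms.

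The cost is one footnote, one derivation rule and one short sensitivity analysis. For affected patients, sites would need to enter the exchange date and a pre-exchange IgM from the file. Treatment, visits and sample size do not change.
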